7.6.4. Vital Signs

Descriptive statistics for each vital sign (eg systolic blood pressure, diastolic blood pressure, pulse rate, body temperature, respiratory rate, height, weight, body mass index) will be summarized at scheduled visits. Summaries will include actual values and changes from baseline. A summary table of potentially clinically significant shifts in vital signs will be generated.

For any patient < 18 years old at screening, a summary table of descriptive statistics of modified z-scores of patient height, weight, and BMI by visits will be generated. A tabular summary of the proportion of patients with z-scores at various cut-points (ie $\geq \pm 2 \text{ SD}$) will also be generated.

A by-patient listing of vital sign data will be generated. Per patient plots of z-scores over time may also be generated.

7.6.5. Physical Examinations

Full physical examinations and symptom-directed physical examinations will be conducted throughout the study. Clinical significant abnormalities observed during the physical

examination are recorded on the medical history or AE eCRF as appropriate. A separate listing per patient will be generated to display the date and time of the physical exam.

7.6.6. **Electrocardiogram**

Electrocardiogram (ECG) parameters include rhythm, ventricular rate, PR interval, QRS duration, QT interval, and QTc interval. Corrected QT interval (QTc), if not collected, will be calculated using the Fridericia's correction formula.

$$\text{Fridericia's cube-root corrected QT: } \text{QTcF (ms)} = \text{QT (ms)} \times \sqrt[3]{\frac{\text{HR(bpm)}}{60}}.$$

The number and percentage of patients with normal, abnormal, and clinically significant abnormal results at baseline and each timepoint will be summarized. For electrocardiogram parameters, these will be summarized using descriptive statistics for actual values and for changes from baseline by scheduled time of evaluation. Baseline, post baseline maximum QTcF and post baseline maximum change from baseline in QTcF during the study will be summarized with descriptive statistics. The incidence of notable ECG changes from baseline in maximum absolute QTcF, intervals (≤ 450 , > 450 , > 480 , and > 500 ms) over all post-treatment evaluations, as well as in QTcF, maximum changes from baseline (≤ 30 ms, $> 30-60$ ms and > 60 ms) over all post-treatment evaluations will be summarized.

A listing of all ECG data will be provided.

7.7. **Anti-Drug Antibody**

The number and associated percentage of patients who have confirmed ADA positive results at baseline and/or any post-baseline visit will be summarized. A listing of patients with ADA positivity with their AEs will be provided.

A listing of all ADA data with associated titers will be provided.

7.8. **COVID-19 Pandemic Impact Analyses**

Additional data were collected to characterize the impact of the COVID-19 pandemic on general study conduct, disposition, and subsequently additional analyses and summaries will be provided in acknowledgement of multiple regulatory guidance (FDA Guidance on Conduct of Clinical Trials of Medical Products during COVID-19 Pandemic: Guidance for Industry, Investigators, and Institutional Review Boards, US Food and Drug Administration, 2020; Statistical Considerations for Clinical Trials During the COVID-19 Public Health Emergency, US Food and Drug Administration, 2020; Guidance on the Management of Clinical Trials during the COVID-19 (Coronavirus) Pandemic, European Medicines Agency, 2020; Points to consider on implications of Coronavirus disease (COVID-19) on methodological aspects of ongoing clinical trials, European Medicines Agency, 2020).

7.8.1. **General Impact**

Patients who discontinue treatment or stop study participation due to the COVID-19 pandemic will be included in patient disposition summaries. Impact on study participation due to the COVID-19 pandemic, including visit completion, visit location changes, and study drug dosing

and location changes, will be summarized overall on the patient level, and overall and by visit on the event level.

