6.5.5.1. Immunogenicity

Blood samples will be collected to evaluate antidrug antibodies. Blood samples for antidrug antibody testing must be collected before study drug administration as specified in the Schedules of Assessment (see Table 1, Table 2, Table 3, and Table 4). A blood sample to evaluate antidrug antibodies will be collected at the Early Termination visit, if applicable.

Details regarding the processing, shipping, and analysis of the samples will be provided in the Laboratory Manual.

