7.2.9. Immunogenicity Analyses

Antidrug antibody results will be summarized descriptively by patient and overall.

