3.3. Exploratory Endpoints

The following are the exploratory endpoints:

- Growth parameters in patients who are < 6 years of age at consent
- Change in developmental milestones over time in patients < 6 years of age at consent
- Change in QoL as assessed by EQ-5D-Y and PedsQL (individual subscales of the generic and ESRD modules, and ESRD module total score) for patients ≥ 2 to 18 years of age at consent, and as assessed by EQ-5D-5L in patients ≥ 18 years of age at consent
- Change in QoL as assessed by KDQOL Symptoms and Problems of Kidney Disease subscale in patients ≥ 18 years of age at consent
- Change in patient and caregiver resource use (eg, work/school attendance, visits to doctor/hospital)
- Change in patient and caregiver experiences as evaluated by a patient experience questionnaire and a caregiver experience questionnaire
- Frequency of ADA
- Change in urinary and plasma glycolate, where urinary glycolate is measured by urinary glycolate:creatinine ratio

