5.4. Baseline Definitions

In Cohort A patients, the plasma oxalate baseline is defined as the mean of all plasma oxalate level values collected prior to the first dose of lumasiran. In Cohort B patients, the plasma oxalate baseline is similarly defined except that the values obtained from the plasma oxalate profile assessment visits will only include the first pre-dialysis sample collected per visit.

For all patients who are not anuric (anuria is defined as <100 ml of urine per day), single-void urine samples (in triplicate) will be collected during screening, with the mean of values for the various parameters measured in these single-void samples used to establish baseline. In these patients, three 24-hour collections will be performed during Screening, with the median values of all the valid samples used to establish baseline urinary oxalate levels.

A 24-hour urine collection will be considered valid if each of the following criteria are met:

- The collection is between 18 to 26 hours in duration between the initial discarded void and the last void or attempt to void.
- No voids are missed between the start and end time of the collection.
- In patients not undergoing dialysis, the 24-hour creatinine content is at least 5 mg/kg for patients <6 years of age, and 10 mg/kg for patients ≥6 years of age as measured in the study central laboratory.

In patients undergoing dialysis, 24-hour collections are not required to have a minimum creatinine content to be considered valid.

Urine data collected from patients that are anuric is considered unreliable; thus there will be no analyses performed for patients that were anuric, from whom urine samples are not collected.

In Cohort B, baseline plasma oxalate AUC measurements will be obtained via the plasma oxalate profile assessments prior to the first dose of lumasiran. Plasma oxalate profile assessments will be performed during Screening, with the mean value of all valid AUC profiles (see Section 7.3.1) being computed to establish the baseline AUC.

For other parameters, baseline is defined as the last non-missing value prior to the first dose date/time of lumasiran, unless otherwise specified. The baseline value for any measurements with multiple values at a visit (eg labs, etc.) will be defined as the mean of all values collected on the most recent date of assessment prior to the first dose date/time of lumasiran.

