7.4.6. Anti-drug Antibody

Analysis of ADA is included in Section [7.7](#).

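### The planned ADA percentage does not isolate treatment-emergent antibodies: patients already positive before the first dose can be counted with those who became positive on lumasiran (minor)

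*SAP*

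**What the plan says.** SAP 3.3 lists "Frequency of ADA" as an exploratory endpoint, without restricting it to antibodies that arise on treatment. SAP 7.4.6 passes the analysis on to section 7.7 ("Analysis of ADA is included in Section" 7.7). Section 7.7 then states that the number and percentage of "patients who have confirmed ADA positive results at baseline and/or any post-baseline visit will be summarized". It adds two listings: ADA-positive patients with their adverse events, and every ADA result with its titre. It names no denominator.

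Protocol 7.2.9 says only: "Antidrug antibody results will be summarized descriptively by patient and overall".

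On timing, protocol Table 1 schedules ADA samples at Day 1, Month 1, Month 3 and Month 6, and protocol 6.5.5.1 states: "Blood samples for antidrug antibody testing must be collected before study drug administration". The general rule in SAP 5.4 for parameters without their own definition is that "baseline is defined as the last non-missing value prior to the first dose date/time of lumasiran, unless otherwise specified". The Day 1 ADA sample is therefore drug-naive and serves as the baseline.

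Neither document defines treatment-emergent, treatment-induced or boosted ADA, sets a titre-rise rule, or restricts any ADA count to patients negative at baseline.

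**The concern.** The protocol's stated purpose for this endpoint is to assess antibodies against lumasiran. The study has no control group, so each patient's own pre-dose sample is the only means of telling pre-existing reactivity or assay background from antibody that appears after dosing. The trial collects that sample, but the one planned summary does not use it to separate the two.

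The rest of the SAP handles this differently. Section 7.6.1 defines treatment-emergent adverse events relative to the first dose. Section 7.6.3 plans shift tables from baseline to the worst later value. The ECG section reports baseline, post-baseline maximum and maximum change separately. ADA has no equivalent.

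What is at stake is how one percentage in the study report is read. With about 20 patients, a single pre-existing positive is enough to make a drug that induced no antibodies appear to have a non-zero ADA frequency.

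**Working it through.** The plan states no ADA rate, so there is no figure to reproduce. The check has three parts.

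**1. What each reading of the sentence counts**

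| Patient | Pooled count | Separate post-baseline row | Treatment-emergent |
|---|---|---|---|
| Positive on Day 1 only | counted | not counted | not counted |
| Positive on Day 1 and later | counted | counted | not counted, unless shown to be boosted |
| Negative on Day 1, positive later | counted | counted | counted |

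Separate rows remove the first discrepancy but not the second. Only a cross-classification by baseline status removes both.

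**2. Size, with complete sampling**

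Inputs: N = 20 planned, at least 6 per cohort (SAP 5.1); all endpoints are analysed by cohort (SAP 7). Let k be the number of baseline positives and n the number of new post-baseline positives. The pooled rate is (k + n)/N. The treatment-emergent rate among baseline negatives is n/(N − k).

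- N = 20, k = 1 (baseline only), n = 0: 1/20 = 5.0% against 0/19 = 0%.
- N = 20, k = 1, n = 1: 2/20 = 10.0% against 1/19 = 5.3%. If the baseline-positive patient stays positive, a separate post-baseline row also reads 2/20 = 10.0%.
- Cohort of 6, k = 1, n = 0: 1/6 = 16.7% against 0/5 = 0%.
- k = 0: both formulas give n/N, so there is no difference from this source.

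Direction: (k + n)(N − k) − nN = k(N − k − n), which is never negative. With complete sampling the pooled rate is therefore never below the treatment-emergent rate.

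That does not carry over to incomplete sampling. SAP 5.5 expects missing blood tests because of blood-volume limits. Suppose 20 treated patients, none positive at baseline, 4 with no post-baseline sample and 1 new positive (assumed counts). Over all treated the rate is 1/20 = 5.0%; over patients with a post-baseline result it is 1/16 = 6.3%. Here the figure over all treated is the lower one.

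**3. How likely a baseline positive is**

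The documents give no baseline prevalence p. Taking p from 1% to 10% as an assumption, the chance of at least one baseline positive is 1 − (1 − p)^N:

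| Assumed p | N = 20 | N = 6 |
|---|---|---|
| 1% | 18% | 6% |
| 2% | 33% | 11% |
| 5% | 64% | 26% |
| 10% | 88% | 47% |

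**The case against.** The best defence is that section 7.7 names two time points where a pooled count could simply have said any visit. This is consistent with separate baseline and post-baseline rows, and the sentence describes content, not a table layout. That stands as far as it goes: the wording is ambiguous, and a reader should not infer that the SAP certainly commits to one pooled count. Separate rows would still leave persistent baseline positives in the post-baseline row.

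Second, a reader might infer that the planned reporting cannot show whether lumasiran induces ADA. The documents do not support that. Every ADA result is listed with its titre, the protocol also summarises ADA by patient, and with 20 patients pre-existing and new positives can be sorted by hand. What the listing does not do is change the summarised percentage.

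Third, a reader might infer that the planned figure can only err upward, or that it must equal the treatment-emergent rate when nobody is positive at baseline. Both hold only with complete post-baseline sampling, as the 1/20 against 1/16 example shows.

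Finally, the endpoint is worded as frequency, not as treatment-emergent incidence, so overall prevalence is a legitimate description of it. Nothing in the documents requires the split, and no hypothesis test, stopping rule or dosing decision depends on it. This is accepted, and it limits the severity.

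**Conclusion.** The point holds as a minor one. Under either programming of section 7.7, the summary percentage does not isolate treatment-emergent ADA. With complete sampling, each baseline-only positive adds 5.0 points to a pooled count at N = 20 when no one converts, or 16.7 points in a cohort of 6. The effect from this source is zero if no patient is positive on Day 1. Whether it arises is unknown, because the documents give no baseline rate and the probabilities above rest on assumed values. The conclusion does not extend to the primary or secondary results, and baseline status remains recoverable from the listing.

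**What to change.** In SAP 7.7, replace the single sentence with three tabulations, each with its denominator:

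- **(a) Pre-existing ADA:** confirmed positive at baseline, over patients with a baseline result.
- **(b) Treatment-emergent ADA, as the headline figure:** negative at baseline and confirmed positive afterwards, over baseline-negative patients with at least one post-baseline result.
- **(c) Baseline-positive patients, shown separately** with their titre change from baseline. Use the label boosted only if a titre-rise threshold is set from the assay's variability; the documents give no such figure.

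(b) and (c) come from different groups, so their percentages cannot simply be added. If a combined figure is shown, use all patients with a baseline and at least one post-baseline result as the common denominator. With 20 such patients, one new positive and one baseline positive, that is 1/20 = 5.0% if the latter is not boosted and 2/20 = 10.0% if it is.

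Also flag baseline-only positives in the listing of ADA-positive patients with their adverse events.

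Cost: SAP wording and minor programming, with slightly smaller denominators. The samples and titres are already planned, so no new procedure is needed.

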7.8.2. Impact on Efficacy

The final analyses will include COVID-19 pandemic impacted efficacy analyses. These analyses will evaluate the impact of changes in the visit windows for the efficacy assessments made in protocol amendment 1 (dated 06 May 2020) due to the COVID-19 pandemic. Missing efficacy data due to the COVID-19 pandemic will be summarized.

For the primary analysis, the primary and secondary endpoints missed or assessed out of the original protocol window will be noted in the efficacy subject listing.

7.8.3. Impact on Adverse Events

An overall summary of AEs mapping to a COVID-19 custom query will include the number and percentage of patients, as well as events and event rates, with any AE, any AE related to study drug, any severe AE, any severe AE related to study drug, any SAE, any SAE related to study drug, any AE leading to treatment discontinuation, any study drug related AE leading to treatment discontinuation, any AE leading to study withdrawal, any study drug related AE leading the study withdrawal, and any deaths. AEs mapping to the COVID-19 custom query will be summarized by high level term and preferred term. Due to the evolving nature of COVID-19-related MedDRA terminology, the COVID-19 custom query will be based on the latest information available at the specified time points. For patients reporting an AE mapped to the COVID-19 custom query, prior medications and concomitant medications will also be presented in separate data listings.

An overall summary of AEs by COVID-19 pandemic phase (ie, pre-, during, post) will include the number and percentage of patients, as well as events and event rates, with any AE and any SAE. Events will be considered during the COVID-19 pandemic if the event occurs on or after the first confirmed case of COVID-19 based on the country where the study site is located, described in Section 10.3.

7.8.4. Other Impacts

Treatment duration may also be summarized by pandemic phase. Protocol deviation due to COVID-19 pandemic will be summarized and will be indicated in the listing of protocol deviations.

8. CHANGES TO PLANNED ANALYSES

Summary of Changes	Rationale
The PK analysis set definition was updated.	The definition in the protocol was updated in the Protocol Amendment 1 dated 06May2020
The Sample Size was modified.	The sample size in the protocol was changed in the Protocol Amendment 1 dated 06May2020
Changes were made in sections 5.5, 5.6, and 7.3.1 to clarify the analyses related to plasma oxalate AUC.	Provided additional details for plasma oxalate AUC related definitions, derivations, and analyses.
Subsections in 7.3 and 7.4 were provided for various endpoints including secondary endpoint analyses during the extension period, exploratory efficacy analyses for the quality of life and patient and caregiver resource use endpoints.	This modification was made to improve readability.
Cardiac Systemic Oxalosis at Month 6 was added to the exploratory endpoints.	To specify the analysis for the primary analysis period.
A section was added for the COVID-19 Pandemic Analyses.	The COVID-19 pandemic occurred after the original SAP.
The COVID-19 Pandemic Phase Start Dates by Country was added to the appendix.	This information was not in the original SAP.
Various editorial changes were made.	To improve clarity

10. APPENDICES

10.1. Medical History Adjustment

Baseline disease history within the preceding year is required at enrollment. For infants less than one year old, reported values may need to be adjusted to represent a medically meaningful baseline value. Below is an example of the adjustment criteria to be used in such situations, for the outcome of renal stone events:

1. Patients less than 6 months old, baseline records will be presented in by-patient listings, however will not be used in summary tables
2. Patients (≥ 0.5 and < 1 year old): Annualized rate will be calculated from reported data ie if a patient of 8 months old has had 2 renal stone events prior to screening, his/her renal stone event rate at baseline will be $2 * (8/12) = 3$ events per year
3. Patients (≥ 1 year old): records at screening for the preceding year will be used to calculate baseline annual stone event rate without adjustment

10.2. Category of Vineland Adaptive Behavior Scale

Vineland adaptive behavior composite scores are collected and summarized using Vineland-II.

The adaptive level of the composite scores can be categorized from “Low” to “High” in the table below.

Adaptive Level of Vineland Composite Scores

Adaptive Level	v-Scale	Standard Score
Low	1 to 9	20 to 70
Moderately Low	10 to 12	71 to 85
Adequate	13 to 17	86 to 114
Moderately High	18 to 20	115 to 129
High	21 to 24	130 to 160

10.3. COVID-19 Pandemic Phase Start Dates by Country

These dates are as reported by the World Health Organization.

Country	Date of 1 st Confirmed Case
Australia	26JAN2020
Belgium	04FEB2020
France	24JAN2020
Germany	28JAN2020
Israel	27FEB2020

Jordan	02MAR2020
Lebanon	21FEB2020
Netherlands	28FEB2020
Switzerland	24FEB2020
Turkey	11MAR2020
United Arab Emirates	01FEB2020
United Kingdom	01FEB2020
United States	20JAN2020
